#### **C3g. Sample size and power considerations**

Based on the sample size calculation using G\*Power, a total sample size of 102 (n=51 for each group) will be sufficient to detect a small effect size ( $f=0.1$ ) in Group (between-subject) by Trial (within-subject: craving ratings for the first and last trials during CE session 2) interaction on craving using mixed (within-between) factorial ANOVA/ANCOVA, with 80% power, an alpha of 0.05, and a correlation coefficient between repeated measures (the first and last trial) of 0.75.

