## **Intervention Modules**

***Abstinence Challenge.*** Eligible participants will be required to abstain from smoking beginning 24 hours prior to the physical exam that occurs on the day of the first CE session and up until the time of the second session. Abstinence status will be verified by a Vitalograph Breathco Carbon Monoxide monitor ( $\leq 4$  ppm). If a participant is not abstinent at the time of the physical exam and CE session 1, the participant will be asked to re-schedule within 1 week. In order to ensure compliance with alcohol abstinence 24 hours prior to CE session 1 and 24 hours after CE session 1, abstinence status will be verified by an AlcoBreath measurement at the beginning of CE session 1 and the beginning of CE session 2. If a participant is not abstinent at the time of CE session 1, the participant will be asked to re-schedule within 1 week.

***Ecological Momentary Assessment (EMA).*** Eligible participants will be asked to respond to surveys delivered via text message or email up to 15 times per day 24-hours prior to the physical exam and up until the time of Cue Exposure Session 2 (48 hours total). Participants will be asked various questions related to smoking craving, behavior, and cues (see attached Short Smoking Log).

***Cue Exposure (CE).*** The two 60-minute CE sessions will be conducted to expose participants to interoceptive and situational cues for tobacco use and craving (see Cue Exposure Therapy Protocol attachment). In the first session, participants will receive a dose of ISR or PBO and begin the CE session after waiting 75 minutes. The overarching goal of CE is to expose participants to triggers that will produce high cravings, and to repeat exposure to those triggers in a controlled setting in order to allow the craving to come down on its own. Because not all smokers respond equally to the same triggers, clinicians are trained to apply a variety of approaches. These can include exposure to slides, videos (on a traditional flat screen as well as in 360 video headsets) depicting smoking cues (visual exposure), exposure to emotions and imagined situations that most reliably triggered an urge to smoke (emotional/imaginal), and exposure to a participant's own cigarettes (in vivo). The second session will be conducted 24 h after the first in a medication-free state. Clinicians will record craving throughout the CE sessions (see Reported Craving During CE attachment).

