***Measures of research integrity, safety, and acceptance***

**Vital Signs.** Participants' blood pressure and heart rate will be assessed. This will be collected during the screening visit, CET visit 1 and 2.

**Patient Adherence.** Patient adherence will be assessed by taking attendance at each session.

**Researcher Adherence.** Each session (for those participants who give consent to be videotaped) will be videotaped and 10% will be rated shortly thereafter by independent raters to assess therapist adherence to, and competence with, the experimental protocol. Participants are not required to be videotaped and will indicate on their ICD whether or not they are willing to participate in the recording of sessions. Sessions from CE visit 1 and 2 will be reviewed.

**Concurrent Treatment.** Use of medications other than nicotine patch or other aids to smoking cessation and participation in any concurrent psychotherapeutic treatment will be assessed. This will be collected during the screening visit, CE visit 1 and 2.

**Safety Monitoring and Concerns.** At each visit, participants will be asked about side effects of the study medication and procedures. Adverse Events forms will be utilized to track any symptoms expressed during study visits. Forms will be reviewed each visit by the study PI, and participants who report significant symptoms or adverse reactions will be interviewed separately. This will be collected during the screening visit, CE visit 1 and 2.

**AlcoBreath Screening.** Participants will be asked to breathe into an AlcoBreath tube in order to assess for the presence of alcohol. Although there are no absolute contraindications to co-administration of isradipine with alcohol, both substances are metabolized through the liver. Participants are advised to refrain from alcohol for at least 24 hours prior to administration of isradipine and 24 hours after administration of isradipine. This will be collected during the screening visit, CE visit 1 and 2.

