## Data Analyses

### Specific Aim 1: Effect on Long Term Craving

To examine effects on the target of engagement, we will test the hypothesis that CE+ISR, compared to CE+PBO, will have a greater reduction in reduce subjective craving to smoking cues in a subsequent medication-free cue exposure conducted 24-hours later (CE 2).

Analytic approach: A mixed factorial ANOVA will be used to test whether reduction in craving over the course of CE session 2 significantly differ across groups (CE+ISR vs. CE+PBO). More specifically, a 2X2 mixed (within-between) factorial ANOVA will be conducted with Group (2 levels: CE+ISR vs. CE+PBO) as the between-subject variable and Trials (2 levels: the first and last trials during the CE session 2) as the within-subject variable to examine the Group X Trial interaction effects on craving. A separate analysis (ANCOVA) for the same model will be conducted, controlling for sex and baseline nicotine dependence. In addition, potential moderating roles of sex and baseline smoking severity on the effect of CE+ISR (vs. CE+PBO) on craving at the first trial during the CE session 2 will be explored by using two-way ANOVA to test the Group X Moderator interactions or linear regression models with Group X Moderator interaction terms.

**Specific Aim 2: Feasibility and Acceptability of Implementation:** Descriptive statistics will be calculated for the questionnaire to assess overall clinic staff views of feasibility, acceptability, and ease of implementation. A qualitative descriptive approach will be used to analyze semi-structured interview transcripts using content analysis to systematically code and categorize for trends and patterns in the textual data to remain as close to the staff's experiences as possible. We have successfully used similar approaches in prior studies.

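### Do the 102 participants need an allowance, and the primary ANOVA a stated rule, for those who lapse before or miss the second cue exposure session?

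*Combined protocol and SAP*

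**What the plan says.** Under C3g (Sample size and power considerations), "a total sample size of 102 (n=51 for each group) will be sufficient". The target is f = 0.1 for the interaction of group and trial. The remaining inputs are power of 80%, alpha 0.05 and "a correlation coefficient between repeated measures (the first and last trial) of 0.75". No allowance for loss is mentioned.

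Under Data Analyses, Specific Aim 1, the primary test is a 2 × 2 mixed ANOVA with treatment group between subjects and "Trials (2 levels: the first and last trials during the CE session 2) as the within-subject variable". No analysis set is named, no exclusion is stated, and missing ratings are not discussed.

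Under Intervention Modules (Abstinence Challenge), smoking abstinence runs from 24 hours before the physical exam that takes place "on the day of the first CE session and up until the time of the second session", with a carbon monoxide limit of 4 ppm. The stated consequence of failure, a new appointment in the following week, covers the start only: "If a participant is not abstinent at the time of the physical exam and CE session 1, the participant will be asked to re-schedule". Alcohol is checked at both sessions, and again a consequence is given for CE 1 alone. The Assessment Schedule lists carbon monoxide and AlcoBreath at CE 2.

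Under the measures of research integrity, "Patient adherence will be assessed by taking attendance at each session". What follows from a missed CE 2 is not stated.

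**The concern.** Both ratings in the primary test come from CE 2. A participant who misses that session has no primary outcome, and one without a last rating drops out of the mixed ANOVA. A participant who smokes between the sessions may give both ratings, but recent smoking can alter the craving being measured.

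The lapse comes after randomisation and dosing. Leaving lapsers out conditions the comparison on a post-randomisation event, while keeping them may dilute a drug effect. The two choices can give different answers, and with no written rule the choice could be made after the data are seen.

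The sample size also has almost no slack. If 102 is the number randomised, any loss of CE 2 data brings power towards or below the stated 80%.

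**Working it through.** **Inputs.** From C3g: N = 102 (51 per arm), f = 0.1, alpha 0.05, ρ = 0.75. From Specific Aim 1: m = 2 repeated measures, two groups.

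**Reproducing the plan's figure.** For the within-between interaction, using the G*Power default convention for the effect size:

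- λ = f² × N × m / (1 − ρ) = 0.01 × 102 × 2 / 0.25 = 8.16
- degrees of freedom 1 and N − 2 = 100
- power from the noncentral F distribution = 80.76%

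Cross-check on change scores, in units of the SD of a single rating. With two groups and two trials, f = 0.1 corresponds to a difference of 4 × 0.1 = 0.40 between the arms' mean changes. The SD of a change is √(2 × (1 − 0.75)) = 0.707, so its variance is 0.5. Then λ = 0.40² / (0.5 × 2/51) = 0.16 × 51 = 8.16, the same value.

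**Slack.**

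| Number with both CE 2 ratings | Power |
|---|---|
| 102 | 80.76% |
| 101 | 80.37% |
| 100 | 79.97% |

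So 102 is the smallest balanced total that reaches 80%, as one expects when a program solves for the minimum. The shortfall at 100 is 0.03 percentage points, which is of no practical weight. Removing two degrees of freedom for the covariates in the ANCOVA leaves 80.74% at 102.

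**If 102 is the number randomised.** The documents give no loss rate, so these rates are assumptions chosen to show a range.

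| Assumed share without CE 2 data | Analysed | Power | Below 80% by | Randomised to keep 51 per arm |
|---|---|---|---|---|
| 5% | 102 × 0.95 ≈ 97 | 78.7% | 1.3 points | 51/0.95 → 54 per arm, 108 |
| 10% | 102 × 0.90 ≈ 92 | 76.5% | 3.5 points | 51/0.90 → 57 per arm, 114 |
| 20% | 102 × 0.80 ≈ 82 | 71.6% | 8.4 points | 51/0.80 → 64 per arm, 128 |

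If 102 is the number analysed, C3g holds as it stands.

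**What the ANOVA does as written.** Specific Aim 1 sets no condition on the carbon monoxide or alcohol reading at CE 2, and nothing else in the text removes a randomised participant from the analysis after dosing. A participant with a first and a last CE 2 rating therefore enters, in the randomised group. One without both ratings cannot enter a two-level repeated-measures ANOVA. The silence thus resolves to one default: all randomised participants with both ratings, whatever the reading.

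**Features that bear on loss.** Treatment is a single observed dose before CE 1, CE 2 follows 24 hours later, and the Day 2 payment is the largest (up to $80, against up to $60 for Day 1). These favour return to the clinic. They say less about lapse, since the Summary of Visits does not tie payment to abstinence.

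**The case for a change.** The best case for a change is that the plan foresees failed abstinence, since it provides for it at CE 1 and measures it again at CE 2, yet gives the CE 2 result no meaning for the data. A default that follows from silence protects less than a written rule: an analyst could still drop lapsers after seeing the results, and writing the rule down would cost a few sentences.

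The silence is real, and so is the risk in principle. The text also leaves open what is done at CE 2 when the smoking or alcohol check fails. That is a matter of conduct for the sponsor to complete, and it may be covered in the Cue Exposure Therapy Protocol attachment, which is not among the documents.

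The rest carries less weight. To drop lapsers, an analyst would have to add an exclusion that Specific Aim 1 does not contain. The written rule one would ask for matches what the ANOVA already does, and it does not cure missing data, because requiring both CE 2 ratings is itself a selection after randomisation.

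Larger power losses than those tabulated appear only if lapsers are kept and assumed to show no drug effect at all. Nothing in the documents supports that, since the dose and CE 1 are complete before any lapse between sessions. It also cannot apply to someone who misses CE 2, who has no ratings to keep.

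**Conclusion.** No change is needed. The sample size is correct under its stated inputs (80.8% at 102), and no stated figure is missed. The gap is one of detail that analysts fill sensibly: the analysis as written includes everyone with both CE 2 ratings in the assigned arm, and an abstinent-only sensitivity analysis with counts of lapse and non-return by arm is a routine addition.

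If 102 is the number randomised, the cost is 1.3 points of power at an assumed 5% loss, 3.5 points at 10% and 8.4 points at 20%. These figures rest on the plan's f and correlation and on loss rates that the documents do not give. With no stated rate, enrolling 108 to 128 is a preference for more margin, not the correction of an error.

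The conclusion also assumes that Specific Aim 1 is applied as it stands, with no exclusion for lapse added later. Saying whether 102 means randomised or analysed would be a useful clarification when the text is next revised.

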#### **D. Limitations and alternative considerations**

While a variety of indirect measures of craving have been proposed for humans, including behavioral indicators (e.g., rate and latency of consumption, inter-puff-interval), psychophysiological measures (e.g., startle eye-blink, skin conductance response, and heart rate) and cognitive measures (e.g., attentional and cognitive biases to drug cues), the advantages of these over subjective report is not clear. Meta-analysis of cue reactivity research show robust increases in subjective craving compared to physiologic indices.

Although functional MRI is a powerful tool for understanding the neural mechanisms of human addiction, it is not feasible for this project. Importantly, treatment research employing prospective analyses and ecological momentary assessment have demonstrated that subjective craving post-cessation and through the abstinence phase is a robust predictor of relapse, indicating the value of a simple, direct, measure of craving and as a potential mechanistic target
